Outcomes research in plastic and reconstructive surgery is more likely to focus on patient reported outcomes than survival. While the plastic surgery literature is replete with surveys focused on judging patient satisfaction, they are infrequently validated or comprehensive. The Breast Q has been established as a validated instrument to provide a quantitative measure of the unique features of patient reported outcomes following breast surgery. This instrument represents the most comprehensive and specific quantitative method for patient self-assessment following breast surgery. Recently, McCarthy and colleagues published, for the first time, patient satisfaction in 41 patients who underwent breast augmentation and were evaluated with the Breast Q. This study found statistically significant improvements following breast augmentation in the "satisfaction with breasts" – 14 item scale, "psychological well-being" – 9 item scale, and "sexual well-being" – 5 item scale. This study does not, however, include information on either the benefits of 3D imaging or the mammometric parameters most closely associated with improved satisfaction. Interestingly, the core scale "satisfaction with care" was not evaluated in this study. While this particular core scale may not have been relevant to a study looking at the overall benefits of breast augmentation, we suspect that it may be highly relevant to the aesthetic surgery patient where the consultation experience is more likely to impact overall patient satisfaction.

This study will evaluate the impact of incorporating 3D imaging during preoperative consultation on patient reported outcomes in primary breast augmentation surgery. 3D imaging can be used to facilitate patient education and surgical planning in the context of breast augmentation. The purpose of this study is to utilize the most objective assessment available for assessing patient satisfaction with breast augmentation - the Breast Q - in a prospective randomized trial. We will evaluate whether 3D imaging used in consultation 1) can improve patient reported outcomes, and 2) whether there are measurable mammometric parameters that are associated with improved patient satisfaction and 3) if utilizing 3D imaging in the pre-operative consultation significantly influences final mammometric parameters compared to patients receiving a traditional consultation that does not involve 3D breast surgical simulation.

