2.2 Secondary Objective

To determine if measureable mammometric parameters are associated with improved patient satisfaction.

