4.2 Randomization

100 patients will be recruited in the randomized cohort. Randomization will be performed by a Research Patient Coordinator and the patient assigned to the control group or the intervention group. Randomization will only occur after the patient has signed the informed consent and will be documented in the case report file as well as communicated to the treating surgeon.

Intervention group

In the intervention group, in addition to standard preoperative evaluation, 3D image simulation will be performed.

Control group

In the conventional group, only the standard preoperative evaluation will be performed.

Non-Randomized cohort

In the non-randomized cohort, the patient can choose to have the standard evaluation with the addition of the 3D image simulation or not based on discussion with their surgeon.

Minimizing measurement bias

Blinding of the patient or surgeon will not be possible due to the need for the 3D imaging simulation to be openly discussed and viewed prior to the operation for patients randomized to 3D intervention and for the nonrandomized cohort.

All subjects will be administered the Breast Q questionnaire prior to surgery regardless of assigned group. The questionnaire will take approximately 5-10 minutes of time to complete.

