7.0 STATISTICAL CONSIDERATIONS

7.1 Study Endpoints

Primary endpoint

BREAST Q Augmentation Module. This includes 6 core items, each with several sub-items. Of the 6 core items, 3 are recently shown to statistically significantly improve in patients undergoing breast augmentation: 1) satisfaction with breasts 2) psychological well-being 3) sexual well being. A fourth, 4) satisfaction with care, however, may be particularly relevant to the discerning aesthetic surgery patient using 3D imaging in consultation. The other core items in this instrument are 5) physical well-being and 6) satisfaction with overall outcome which will also be recorded.

Secondary endpoints

All patients will undergo standard 2D as well as 3D imaging before and after surgery. During consultation, and in the postoperative period, reviewing 3D imaging and morphing software will be unique to the experimental group. 3D imaging from all patients will be used to obtain mammometric data. Pre- , and post- op mammometric data (volumes, vectors, surface distances, anatomic landmarks), as well as the measurable change in these parameters before and after surgery will be correlated with changes in Breast Q patient reported outcomes scores. This will enable us to identify particular mammometric parameters that are a) associated with improved patient reported outcomes and b) determine whether certain mammometric parameters are significantly different in patients who had 3D image simulation as part of their preoperative consultation relative to those that did not.

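### The 3D-versus-control comparisons are not expressly confined to randomised patients by assigned arm, and Protocol 4.6 could lose outcomes from the 3D arm only

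*Protocol*

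**What the plan says.** **Endpoint (b).** Protocol 7.1 aims to "determine whether certain mammometric parameters are significantly different in patients who had 3D image simulation as part of their preoperative consultation relative to those" who did not have it. Earlier in the same paragraph it says that "3D imaging from all patients will be used to obtain mammometric data", and also that "reviewing 3D imaging and morphing software will be unique to the experimental group". Protocol 1.0 puts the same question in causal terms: "if utilizing 3D imaging in the pre-operative consultation significantly influences final mammometric parameters compared to patients receiving a traditional consultation". The only secondary objective, in 2.2, is "To determine if measureable mammometric parameters are associated with improved patient satisfaction".

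**Who can receive simulation.** Protocol 4.2 says of controls: "In the conventional group, only the standard preoperative evaluation will be performed". Of the non-randomised cohort it says "the patient can choose to have the standard evaluation with the addition of the 3D image simulation or not". Its paragraph on measurement bias describes the simulation as "openly discussed and viewed prior to the operation for patients randomized to 3D intervention and for the nonrandomized cohort". Appendix B, footnote 3, restricts simulation to the randomised intervention arm.

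**Analysis.** Protocol 7.2 gives the cohort's data to the secondary objective, and 7.3 caps the cohort at 50. Protocol 7.4 compares patients *assigned* to 3D with those who *had* conventional techniques, and names no analysis set. The SAP names tests for patient-level and breast-level comparisons but no groups, population or assignment rule.

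**Removal.** Under Protocol 4.6, a patient who no longer wants the protocol intervention is taken off study. Receiving the intervention and being followed up are described only for everyone else.

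**The concern.** Protocol 1.0 asks whether simulation changes the final result. Randomisation answers that only if patients are compared as assigned. Grouping by who had simulation lets the wish for it, or the willingness to accept it, into the comparison. The regression in 7.4 can adjust only for factors that were measured. If the cohort were included as well, up to a third of the patients (50 of 150) would have chosen their own group.

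The removal rule raises a related problem for Breast Q as well as for mammometrics. If decliners leave the study, those who remain in the 3D arm are a selected subset, while the control arm stays whole.

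**Working it through.** **1. Reading the text.** The passages bear on endpoint (b) as follows.

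| Place | Points towards |
|---|---|
| 7.1, simulation unique to the experimental group | randomised arms |
| 7.4, *assigned* to intervention; 4.2 calls the control arm the conventional group | randomised arms |
| 7.2 read with 2.2: cohort data serve the association question | randomised arms |
| Appendix B, footnote 3 | randomised arms |
| 7.1 and 1.0, wording by receipt or use | by receipt |
| 7.1, imaging from all patients; (b) listed under secondary endpoints | cohort could be included |
| 4.2, cohort may choose simulation | cohort could supply both sides |
| SAP | silent |

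The balance favours the randomised arms. No sentence states it.

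**2. Size.** The plan gives no error rate or detectable difference for endpoint (b), so there is no figure of its own to reproduce. From the documents: 50 per arm and up to 50 in the cohort (7.3), and a two-sided 0.05 level (7.4). Assumed, because the documents give none: uptake in the cohort, decline rate, and selection gap d in SD units (0.2 or 0.5). The true simulation effect is set to zero, with one observation per patient.

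With bias b and SE = √(1/n₁ + 1/n₀), the false-positive rate is P = Φ(−1.96 + b/SE) + Φ(−1.96 − b/SE).

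*(i) Cohort pooled by receipt.* Of 50 cohort patients, k choose 3D and differ by d; non-choosers are taken to equal randomised patients. n₁ = 50 + k, n₀ = 100 − k, b = kd/(50 + k).
- k = 25, SE 0.163: b = 0.067 gives P = 6.9% (d = 0.2); b = 0.167 gives 17.5% (d = 0.5).
- k = 10, SE 0.167: b = 0.033 gives 5.5%; b = 0.083 gives 7.9%.
- k = 0, or no pooling: 5.0%. Uptake above 25 would give more.

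*(ii) By receipt within the 100 randomised.* A share c of each arm is of the declining type and differs by d; those in the 3D arm are counted with controls. n₁ = 50(1 − c), n₀ = 50(1 + c), b = 2cd/(1 + c).

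| c | b, P at d = 0.2 | b, P at d = 0.5 |
|---|---|---|
| 5% | 0.019, 5.1% | 0.048, 5.7% |
| 10% | 0.036, 5.4% | 0.091, 7.4% |
| 20% | 0.067, 6.2% | 0.167, 12.9% |

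*(iii) Removal under 4.6.* A fraction f of the 3D arm is lost. n₁ = 50(1 − f), n₀ = 50, b = fd.

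| f | P at d = 0.2 | P at d = 0.5 |
|---|---|---|
| 5% | 5.0% | 5.2% |
| 10% | 5.1% | 5.7% |
| 20% | 5.4% | 7.6% |

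For the same decliners, (ii) and (iii) are alternatives and do not add.

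**3. Limit of the model.** The SAP plans GEE on both breasts for breast-level comparisons. At an assumed left–right correlation of 0.5, the SE shrinks by √((1 + 0.5)/2) = 0.866. In case (i) with k = 25 and d = 0.5, b/SE rises from 1.02 to 1.18 and P from about 18% to about 22%. Analysing pre-to-post change could instead shrink the gap.

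**The case against.** The strongest reply is that endpoint (b), read in context, already means the randomised arms. Its own paragraph makes simulation unique to the experimental group, 7.4 speaks of assignment, 7.2 with 2.2 points the cohort at the association question, and Appendix B agrees. The SAP is a single paragraph that names no groups for any comparison, so its silence says nothing particular about (b). Its model of enrolment to the randomised arm needs both cohorts in the data, but that does not imply pooling them for outcomes. This reply stands as to likely intent. A reader might infer that the plan commits to an as-treated or pooled analysis; the documents do not support that. What remains is that two analysts could follow the text and run different comparisons.

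On 4.6, a reader might infer that outcome collection from decliners definitely stops. The section implies this but does not state it. Its health-related ground for removal could apply in either arm. Decliners may also be few, because Appendix B puts randomisation and simulation at the same stage and patients who refuse randomisation can join the cohort. So the most that can be said is that data *could* be lost from one side.

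Finally, the sizes are assumed throughout, and the endpoint is secondary, covers many parameters, and sits in an analysis that 7.4 calls descriptive. That limits the weight of the point but does not remove it.

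**Conclusion.** The point holds at modest weight, with medium confidence. The documents do not expressly limit the 3D-versus-control comparisons to randomised patients by assigned arm, and 4.6 as worded could remove outcomes from the 3D arm alone. Neither a pooled nor a by-receipt analysis is shown to be planned.

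The inflation is small at a 0.2 SD gap in every scenario, at most about 7%. It becomes material only at a gap near 0.5 SD, with substantial pooling (up to about 18%) or with 20% of the 3D arm missing simulation and counted as controls (about 13%). The 4.6 effect is small throughout, at most 7.6%. These figures illustrate possible size and do not estimate what will happen.

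The statements on whether the cohort may receive simulation do conflict: 4.2 allows it, while 7.1 and Appendix B confine it to the intervention arm. That needs reconciling on any reading, because it decides whether the cohort can supply patients to the simulation side at all.

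**What to change.** - **Protocol 7.1, 7.4 and the SAP:** state that every 3D-versus-control comparison, for Breast Q and for endpoint (b), uses randomised patients by assigned arm. Include those with surgery and 6-month data, and report missing outcomes by arm.
- **Non-randomised cohort:** use it only for the association between mammometrics and satisfaction, or report it separately. Label any by-receipt comparison exploratory.
- **Protocol 4.6:** separate not receiving simulation from withdrawing consent to follow-up. With consent, keep collecting the 6-month Breast Q and images from the former and analyse them as assigned.
- **Protocol 4.2, 7.1 and Appendix B:** reconcile whether the cohort may receive simulation.

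**Cost.** The change is wording, with no new visits or patients. Following decliners takes a little more effort, and keeping them in their assigned arm dilutes the effect somewhat. Precision is lost only if pooling had been intended. With one observation per patient and 80% power, the detectable difference is 2.80 × √(2/50) = 0.56 SD for 50 v 50, against 2.80 × √(2/75) = 0.46 SD for a pooled 75 v 75.

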1.0 BACKGROUND AND RATIONALE

Advances in 3D breast imaging. Three-dimensional imaging, extensively utilized to provide objective outcome measures in craniofacial surgery, has been adapted for evaluation of the breast. Three-dimensional images of the breast can be used to facilitate patient education, surgical planning, as well as both a research and marketing tool by plastic surgeons. Over the past few years, investigators have identified breast measurements calculated from computerized renderings of three-dimensional photographs and documented changes in these measurements following surgical procedures such as breast reduction, breast reconstruction with implants, and breast augmentation. Changes in these parameters after operative intervention have enabled surgeon scientists to compile objective quantitative breast data, or "mammometrics" (1). Mammometric data can be statistically analyzed, longitudinally evaluated in the same patient over time, and correlated with other quantitative data including patient reported outcomes. Some of the useful mammometric measurements that can be used to quantify and compare pre- with postoperative breast surgery include total and split breast volumes, distances from the low breast crease to the nipple, and projection of the breast and nipple from the chest wall among others.

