7.4 Data Analysis

Data analysis for this study will be descriptive in nature. Demographic and clinical characteristics of the sample, as well as post-surgery complications will be summarized using descriptive statistics and the confidence intervals will also be provided.

[figure not shown]
Patients assigned to the intervention group (3D simulation) will be compared with those who had conventional techniques using χ^2 tests for categorical variables and Student's t-tests for continuous variables. For the t-tests equal variances were not be assumed, unless significant by Levene's test. Mann-Whitney U tests will be utilized for non-normally distributed variables. Two-tailed P values 0.05 will be considered statistically significant.

Multivariate analyses for Breast Q scores, mammometric parameters, and patient satisfaction will be performed using binary logistic regression and linear regression models to examine the relationship between intervention groups and examined outcomes and to identify potential confounders. The results of multivariate analyses will be expressed as odds ratios with corresponding 95% confidence intervals. All analyses will be performed using SPSS 20.0 statistical software (SPSS Inc. Chicago, IL).

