3D Breast Imaging for Cosmetic and Reconstructive Breast Surgery: Does 3D Improve Patient Reported Outcomes in Primary Breast Augmentation?

NCT01964105

AUGUST 27, 2014

The trend of enrolling to the randomized arm of our study will be modeled using the LOGISTIC procedure with maximum likelihood estimation. Predicted probability will be obtained from this model to facilitate clear interpretation of non-linear relationships with time. For patient- level comparisons, the assumption of normality will be examined with the Shapiro-Wilk test after which a t-test or Wilcoxon test will be used as appropriate. When using the t-test, equality of variances will first be examined with the Folded F statistic. The pooled t-test will be used for two populations with equal variances. Otherwise the Satterthwaite t-test will be used. Breast-level comparisons will be performed using generalized estimating equations (GEE) and empirical standard error estimates to account for correlation of left and right breast measurements within the same patient. The Pearson or Spearman correlation coefficient will be used to quantify the direction and magnitude of association between mammometric, Q-Score, and clinical data. Statistical analyses will be performed in SAS, version 9.4, with descriptive statistics analyzed and graphed in Prism 7 for Mac.

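### Secondary endpoint 7.1(b) compares an open list of mammometric parameters between arms at an unadjusted 0.05, with no deciding parameter, no fixed form and no baseline adjustment

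*Protocol*

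**What the plan says.** - **The question.** Protocol section 1.0 gives as the third of three questions "if utilizing 3D imaging in the pre-operative consultation significantly influences final mammometric parameters", compared with a traditional consultation. Section 7.1, part (b) of the secondary endpoints, turns this into an endpoint: to "determine whether certain mammometric parameters are significantly different in patients who had 3D image simulation as part of their preoperative consultation". Section 2.2 lists only the association of mammometrics with satisfaction.
- **The parameters.** Section 7.1 names four classes without members. Section 1.0 gives examples: total and split volumes, then "distances from the low breast crease to the nipple, and projection of the breast and nipple from the chest wall among others". The list is open.
- **The form.** The sentence in 7.1 that covers "Pre- , and post- op mammometric data (volumes, vectors, surface distances, anatomic landmarks), as well as the measurable change in these parameters" concerns correlation with Breast Q change, which is part (a). Part (b) fixes no form. The only pointer is the word for final values in section 1.0.
- **The criterion.** Section 7.4 states: "Two-tailed P values 0.05 will be considered statistically significant". It opens by calling the analysis descriptive, then specifies chi-squared, t and Mann-Whitney tests between the assigned groups.
- **The SAP.** Breast-level comparisons use GEE with empirical standard errors to handle left-right correlation within a patient. It gives no covariates, hierarchy or multiplicity rule.

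**The concern.** An arm comparison in a randomised trial carries causal weight. Here the list of outcomes is open, no member of it is marked as deciding, and each is tested at 0.05. The more measures are tested, the more likely it is that at least one differs by chance. Such a result could be reported as an effect of 3D simulation on the surgical outcome, because section 1.0 puts the question in terms of significant influence.

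Two further gaps add freedom after the data are seen. The form of the outcome is open, although a preoperative value is collected for every patient and could be adjusted for. The population is also not settled. Part (b) is worded by who had simulation, and section 4.2 lets non-randomised patients choose it. Section 7.2 sends their data to the secondary objective, while section 7.4 compares patients by assigned group.

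**Working it through.** The documents state no overall error rate for these comparisons, so there is no figure of the plan's own to reproduce. The sample-size statement in 7.3 concerns patient satisfaction. Only its 50 per arm is used here.

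**Inputs**
- Per-test level 0.05, two-sided, critical value 1.96 (section 7.4).
- Number of measures k = 5: total volume, split volume, crease-to-nipple distance, breast projection and nipple projection. This is my count of the examples in section 1.0. That list is open and partly plural, so five is an assumption.
- One form per measure, the postoperative value (section 1.0, final values).
- Equal correlation r between the test statistics, assumed 0.5, range 0.2-0.8.
- No true effect of simulation on any measure.

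**Step 1. Independent tests, as an upper reference.** 1 - 0.95^5 = 1 - 0.774 = 22.6%.

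**Step 2. Correlated tests.** Write each statistic as Z_j = sqrt(r)·G + sqrt(1-r)·E_j, with G and E_j independent standard normal. Find the probability that any |Z_j| exceeds 1.96.

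| Measures | r = 0.2 | r = 0.5 | r = 0.8 |
|---|---|---|---|
| 4 (one per class in 7.1) | 18.0% | 15.6% | 11.4% |
| 5 (examples in 1.0) | 21.8% | 18.3% | 12.7% |
| 8 (assumed) | 31.9% | 25.0% | 15.8% |

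For five measures this is about 18% (13-22%).

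**Step 3. What adjustment for the preoperative value gains.** Take 50 per arm, 80% power and one value per patient.
- Unadjusted: (1.96 + 0.842) × sqrt(2/50) = 2.802 × 0.2 = 0.56 SD.
- Adjusted, with pre-post correlation 0.5 (assumed): 0.56 × sqrt(1 - 0.5²) = 0.56 × 0.866 = 0.49 SD.
- With pre-post correlation 0.3 or 0.7: 0.53 or 0.40 SD.

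The adjustment improves precision. It does not reduce the error rate in step 2, which depends on how many measures can carry the claim.

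**Step 4. Preoperative values.** Appendix B places photography at screening, before randomisation. A preoperative difference between randomised arms is therefore chance, and a significance test of it says nothing about simulation.

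**The case against.** **The analysis is called descriptive.** This is the most direct defence. It would hold if estimates and intervals were all that followed. Section 7.4 goes on to prescribe tests and a threshold, and sections 1.0 and 7.1(b) ask about significance, so the label does not settle the matter.

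**No rule says that one significant parameter answers the question.** This stands. Part (b) can be read parameter by parameter. The percentages above hold only if a reader or author takes any single significant result as a yes.

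**The forms.** A reader might infer that preoperative, postoperative and change values are all tested between arms. With five measures and correlations of 0.5, that would give about 39%, or about 31% for postoperative values and change. The documents do not support this. The three forms are listed for the correlation with Breast Q, and section 1.0 points to final values for the arm comparison.

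**Parameters were named.** Section 1.0 does single out superomedial pole fullness and central nipple position, but for their association with Breast Q scores, not for the arm comparison.

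**It is only secondary.** This also stands. Unadjusted secondary comparisons are common, and the remedy should be in proportion.

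**Conclusion.** The point holds for a secondary endpoint. Part 7.1(b) has no deciding parameter, fixed form, baseline adjustment or multiplicity rule, and the SAP's GEE deals with paired breasts rather than with many measures. If any single significant parameter were read as a positive answer, the false-positive chance would be about 18% (13-22%) against a nominal 5%. That figure rests on an assumed five measures, postoperative values only, and correlations of 0.2-0.8. With four to eight measures the range is about 11-32%.

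A reader might infer that the trial's main conclusion is at risk. It is not: the primary Breast Q comparison is unaffected, and this question is not among the objectives in section 2. What is at stake is over-claiming a secondary finding.

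**What to change.** In section 7.1(b) and the SAP:

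1. Limit the arm comparison to randomised patients, by assigned group, and to the 6-month value. Fit it in the planned GEE with arm and the preoperative value of the same measurement. Make no significance tests of preoperative values or of raw change. The images are already scheduled, so this needs only a change of wording, and it improves precision (about 0.56 to 0.49 SD at a pre-post correlation of 0.5).
2. Have the investigators name in advance one parameter that alone can support a claim that simulation significantly influences the final result.
3. Report all other mammometric arm comparisons as exploratory, as estimates with 95% confidence intervals.

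The cost of items 2 and 3 is that a difference in any other parameter can be described but not claimed. No adjustment of the 0.05 level is needed for the single named parameter.
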